**Design and Implementation of a Nutritional Intervention in
Patients With Oropharyngeal Dysphagia**

NCT02959450

October 10th, 2021

Patients of 18 years and older, both genders, who had a primary caregiver and a confirmed diagnosis of OD were included. Eating Assessment Tool (EAT-10) and Volume- Viscosity Swallow Test (V-VST) were performed by a clinical nutritionist in order to evaluate the safety and efficacy of swallowing and confirm the diagnosis of OD; select the type of viscosity and volume appropriate for the prescription of the texture-modified diet. Patients with cancer, kidney or hepatic failure, terminally ill patients, as well as high risk of aspiration, reporting a decrease in oxygen saturation $>5\%$ in the V-VST, or with enteral nutrition (EN) through a nasoenteral tube or gastrostomy were excluded. We estimated a sample size of 50 patients per group by the formula of survival of Argimon et al , with an alpha level of 0.05 and more than 90% power to detect a difference of 15% of mortality between groups.

Anthropometry

Anthropometric measurements were performed according to the reference manual for anthropometric standardization. The same scale was used for all patients at each visit. Forearm circumference was measured at the midpoint of the right arm and calf circumference was measured in a supine position with the tape along the calf to measure the greatest circumference without compressing the subcutaneous tissue.

Mini Nutritional Assessment

The nutritional risk was assessed using the Mini Nutritional Assessment (MNA) questionnaire, a valid and reliable tool to identify malnutrition in elderly people. The original version of this tool was used for this study contained 18 questions with a maximum of 30 points. It is considered that a score lower than 17 points represents malnutrition, between 17 and 23.5 points of risk of malnutrition and more than 24 points that the patient is well nourished.

Dietary intake

For the evaluation of the quality and quantity of dietary intake, a 24-hour multiple-step recall was applied and the Food Processor Nutrition Analysis® software was used for the detailed nutritional analysis.

Body composition

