Subjects were randomly allocated to intervention group (modified consistency diet, with a nectar or pudding viscosity) or control group (standard treatment) using a blocked allocation strategy. The *control group* received a traditional modified texture diet, with pureed foods and one viscosity of thickened drinks. The viscosity beverages were not systematically controlled. For the *intervention group* a chef and a clinical nutritionist developed the texture- modified foods and thickened drinks diet, with nectar or pudding viscosity and controlled bolus volume. The foods were thickened using Enterex Food Thickener, Victus® and the viscosity of menus was standardized and measured with a Brookfield Viscometer (model RV). The menus with nectar consistency had a viscosity of 51-350 centipoises (cP) and the pudding consistency foods with a higher viscosity at 1,750 cP. The viscosity of the diet was prescribed according to the viscosity and volume tolerated in the V-VST. A recipe book for caregivers and patients was made to facilitate the preparation of the diet with the exact amount of thickener to use in each menu to achieve the desired viscosity. Training was also provided to patients and caregivers by a video on the use of food thickener (modified ediblestarch) on each menu.

The primary outcome was the amount of energy (kcal/kg) and protein (g/kg) consumed, the secondary outcome was body composition and muscular functionality. The follow-up was carried out in 5 visits during 12 weeks. Adherence to the prescribed meal plan was evaluated at each visit. To evaluate the adherence, it was necessary to have an intake of more than 80% of the nutritional requirements with 24-hour recall. If the intake was lower than indicated, oral nutritional supplements were prescribed to meet the nutritional requirements established in both groups.

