**Design and Implementation of a Nutritional Intervention in
Patients With Oropharyngeal Dysphagia**

NCT02959450

October 10th, 2021

Statistical analysis

The data are presented as mean \pm standard deviation or median with interquartile range [25th- 75th percentile], depending of data distribution. The Shapiro-Wilk test for proper parametric or non-parametric test was performed. Differences between groups at baseline were evaluated with Student's t-test or U Mann-Whitney test for continuous variables and proportions were compared using the Chi2 or Fisher test. Two analyses were performed to evaluate the effect of the nutritional intervention: an intention-to-treat analysis (considering all of the participants) and per-protocol analysis (considering participants who finished the follow-up). Missing data were imputed with the multivariate imputation. For the intention- to-treat analysis, we imputed five complete data sets and pooled the results for the analysis. For post-intervention comparison within-groups, a paired Student-t or Wilcoxon matched-pairs signed rank tests were performed. Also changes between baseline and final intervention in oral intake, body weight and HGS were obtained between groups and were compared with the Mann-Whitney U test, according to the nonparametric distribution of the data. A p-value <0.05 was considered statistically significant. The data were analyzed using the Statistical Package for the Social Sciences (SPSS®) version 25.

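### The between-group test of the primary intake outcome ignores the baseline value as a covariate and leaves out the interim recalls already taken

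*SAP*

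**What the plan says.** The protocol (Nutritional intervention, last paragraph) states: "The primary outcome was the amount of energy (kcal/kg) and protein (g/kg) consumed". Under Dietary intake, the instrument is a recall: "a 24-hour multiple-step recall was applied".

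On timing, the protocol says: "The follow-up was carried out in 5 visits during 12 weeks". It adds: "Adherence to the prescribed meal plan was evaluated at each visit". The yardstick for adherence is again the recall: "it was necessary to have an intake of more than 80% of the nutritional requirements with 24-hour recall". The result has a consequence for the patient: "If the intake was lower than indicated, oral nutritional supplements were prescribed to meet the nutritional requirements established in both groups". Recalls must therefore exist, and be quantified, at the interim visits.

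The SAP (Statistical analysis) describes one post-baseline between-group comparison of intake: "changes between baseline and final intervention in oral intake, body weight and HGS were obtained between groups", and these "were compared with the Mann-Whitney U test, according to the nonparametric distribution of the data". The within-group tests are paired tests after the intervention. The SAP describes no repeated-measures model, no averaging of recalls and no baseline-adjusted comparison. Missing data are imputed in five data sets for the intention-to-treat analysis, but the variables in the imputation model are not listed.

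**The concern.** A 24-hour recall reflects one day and is a noisy measure of usual intake. A change score built from two such measures carries the noise of both. If the two are only moderately correlated, subtracting baseline adds more noise than it removes, whereas using baseline as a covariate cannot do worse on average in a randomised comparison.

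The interim recalls are a second unused source. If the baseline visit is one of the five, three of five recalls stay out of the comparison; if baseline is separate, four of six do. They cost nothing further to collect. They are also the natural information about the final intake of patients who leave early.

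This matters more because the 50 per group was derived from a mortality difference (Protocol, opening paragraph). Nothing in the documents shows what intake difference the trial can detect.

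**Working it through.** **The plan's own figure.** None exists for the precision of the intake comparison. The 50 per group rests on a 15% mortality difference with the control rate and sidedness unstated, and has no bearing here beyond supplying n.

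**Inputs**
- n = 50 per arm (Protocol).
- Five visits (Protocol). I assume the first is baseline, leaving four post-baseline recalls.
- Assumed, because the documents give no value: equal variances, the same correlation r between all recalls, complete data, and comparison on the mean scale.

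**Formulas**, in units of the single-recall variance:
- Change score: 2(1 − r)
- Final recall adjusted for baseline: 1 − r²
- Mean of the last two recalls adjusted for baseline: (1 + r)/2 − r²
- Detectable difference at 80% power, two-sided 0.05: 2.80 × √(2/50 × V)

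**Results at r = 0.5**

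| Analysis | Variance V | Detectable difference (SD of one recall) |
|---|---|---|
| Change score (planned contrast) | 2 × 0.5 = 1.00 | 2.80 × √0.040 = 0.56 |
| Adjusted final recall | 1 − 0.25 = 0.75 | 2.80 × √0.030 = 0.485 |
| Adjusted mean of last two | 0.75 − 0.25 = 0.50 | 2.80 × √0.020 = 0.40 |

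The last row assumes that the effect is the same at both visits.

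**Range for baseline adjustment.** The ratio of the second row to the first is (1 − r²)/(2(1 − r)) = (1 + r)/2. That is 0.60 at r = 0.2, 0.75 at r = 0.5 and 0.90 at r = 0.8, so it is below 1 for every r below 1. This gain uses no interim recall.

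**Does averaging survive if the effect builds up?** Take 25%, 50%, 75% and 100% of the final effect at the four visits.
- The last-two mean keeps (75 + 100)/2 = 87.5% of the effect. Its standard error relative to the adjusted final recall is √(0.50/0.75) = 0.816. Signal-to-noise is 0.875/0.816 = 1.07, a gain of about 7%.
- The mean of all four has variance (1 + 3 × 0.5)/4 − 0.25 = 0.375 and keeps 62.5% of the effect. Signal-to-noise is 0.625/√(0.375/0.75) = 0.88, a loss.

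**Does it survive unequal correlation?** Suppose the last two recalls correlate 0.7 with each other and each correlates 0.3 with baseline.
- Last-two mean, adjusted: (1 + 0.7)/2 − 0.09 = 0.76. Adjusted final recall: 1 − 0.09 = 0.91. Change score: 2 × 0.7 = 1.40.
- With linear build-up, last-two against adjusted final: 0.875/√(0.76/0.91) = 0.96, a loss.
- With linear build-up, last-two against the planned change score: 0.875 × √(1.40/0.76) = 1.19, a gain.
- Adjusted final recall against the planned change score: √(1.40/0.91) = 1.24, without averaging.

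In this case baseline adjustment supplies the whole gain and averaging gives some of it back.

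**The case against.** **The end-of-intervention change is a coherent target.** This stands. Moving the primary outcome to an average over visits would change the question. A repeated-measures model with a final-visit contrast keeps the question as it is. With complete data, that contrast gains essentially nothing over baseline adjustment of the final recall alone; the interim recalls help it only through patients with a missing final value.

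**The interim recalls influence later treatment.** This stands too. A low recall leads to supplements in both arms, so an average of the last two visits can mix intake before and after such a prescription. The final recall can also reflect earlier supplements, so the plan needs to say what counts as intake whichever analysis is used.

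**The data were judged non-normal, hence the rank test.** The variances above are therefore indicative only. Non-normality is no reason to leave out baseline, and the rank test can be kept as a sensitivity analysis.

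**Stronger readings that the documents do not support.** A reader might infer that most of the intake data is thrown away. The recalls serve the adherence check and may already enter the imputation, whose variables are not listed. A reader might credit the full fall from 1.00 to 0.50 to the unused recalls. Half of it is baseline adjustment. A reader might conclude that using more recalls always sharpens the result. The figures 0.88 and 0.96 show otherwise. Finally, the documents do not say how many recall days each visit covered, and the SAP labels no test as primary; that role is inferred because this is the only such test of intake.

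**Conclusion.** The point holds as one of avoidable imprecision. The planned contrast is unadjusted for baseline and omits interim recalls that the protocol implies were taken.

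The firm part is baseline adjustment: under equal variances it reduces the variance at any correlation below 1, by 25% at the assumed 0.5. The conditional part is averaging the last two recalls. It takes the variance to 0.50 with a constant effect, is worth about 7% in signal-to-noise under linear build-up, and may turn into a small loss when neighbouring recalls are more alike than distant ones. The benefit for patients who leave early is real in principle but cannot be sized, because the documents give no dropout figure.

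The correlation, the variances and the time course are all assumptions. Nothing here suggests that the planned comparison is biased.

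**What to change.** - Compare energy and protein intake between arms with a repeated-measures model on all post-baseline recalls, with the baseline recall as covariate. Take the final-visit contrast as the main estimate, which keeps the end-of-intervention target.
- List the variables in the imputation model and include the interim recalls among them.
- Report the baseline-adjusted mean of the last two visits as a supportive analysis.
- State whether intake from supplements counts towards the outcome.
- State whether baseline is one of the five visits.

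No new recalls are needed. The cost is SAP wording and slightly more analysis and, for the supportive average only, a shift of the estimand to the last two visits. Both documents are written in the past tense. If the data have already been analysed, the new model should be labelled a reanalysis and shown beside the planned test.

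### Primary intake outcome: the only post-baseline comparison of arms is an unadjusted Mann-Whitney test on change, with no between-group difference and confidence interval; adding a baseline-adjusted analysis is a cheap improvement

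*SAP*

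**What the plan says.** The last paragraph of the Protocol's Nutritional intervention section states: "The primary outcome was the amount of energy (kcal/kg) and protein (g/kg) consumed". Under Dietary intake, intake is measured as follows: "a 24-hour multiple-step recall was applied".

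The SAP's Statistical analysis section tests continuous variables in three places: between arms at baseline, within each arm before and after the intervention, and between arms on change. Only the third compares the arms after baseline. There, "changes between baseline and final intervention in oral intake, body weight and HGS were obtained between groups", and these "were compared with the Mann-Whitney U test, according to the nonparametric distribution of the data". No covariate or model is named.

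Results are described by mean with "standard deviation or median with interquartile range", and the criterion is "A p-value <0.05 was considered statistically significant". No between-group difference with a confidence interval is mentioned. For the intention-to-treat analysis, "we imputed five complete data sets and pooled the results for the analysis"; neither the pooled quantity nor the rule is given. A per-protocol analysis of those who finished follow-up is also planned.

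I take oral intake in the SAP to mean the energy and protein intake of the Protocol.

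**The concern.** Three things are left undone for the primary outcome.

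- **Baseline intake is used only by subtraction.** It must have been collected, because change is computed from it. A change score fixes the baseline coefficient at 1. When a measurement correlates only weakly to moderately with its own later value, that coefficient is too large, and the change score carries extra noise. A single 24-hour recall may well behave this way, but the documents give no correlation.
- **The size of the effect has no stated precision.** A crude difference can be read from the arm summaries. Nothing planned shows how precisely the arm difference in kcal/kg or g/kg is known.
- **The pooled result is not defined.** Rubin's rules combine an estimate with its variance. A Mann-Whitney U and its p-value are not such a pair, although the probability P(X>Y) with its variance is.

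At stake are power and interpretability for the primary comparison. Validity is not in question.

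**Working it through.** **Inputs.** From the Protocol's opening section: "We estimated a sample size of 50 patients per group". That number was derived for a mortality difference. It cannot be reproduced as a single figure, because the arm rates and sidedness are not given, and it does not bear on intake; I use it only as n. The documents give no intake SD, baseline-final correlation (rho), distribution or missing-data rate, so all of these are assumed over a range.

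**Step 1: normal theory.** With equal SDs at both visits, in units of that SD, the per-patient variance is 2(1−rho) for a change score and 1−rho² with baseline adjustment. The ratio is (1+rho)/2. Power for a 0.5 SD difference, two-sided 5%, is Φ(0.5/√(2v/50) − 1.96). For example, at rho = 0.5:

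- change score: v = 1.00, SE = √(2/50) = 0.200, power = Φ(2.50 − 1.96) = 0.71
- adjusted: v = 0.75, SE = √(1.5/50) = 0.173, power = Φ(2.89 − 1.96) = 0.82

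| rho | variance ratio | power, change v adjusted | n per arm for change to match 50 adjusted |
|---|---|---|---|
| 0.3 | 0.65 | 0.56 v 0.75 | 77 |
| 0.5 | 0.75 | 0.71 v 0.82 | 67 |
| 0.7 | 0.85 | 0.90 v 0.94 | 59 |

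This is not the power of the planned Mann-Whitney test, so that was simulated.

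**Step 2: simulated power, complete data.** 50 per arm, 4,000 replicates, 0.5 SD shift. Shapes: normal; log-normal with sigma 0.4 (mild skew) and 0.8 (strong skew); t with 3 df. Tests: Mann-Whitney on change / linear ANCOVA with HC3 standard errors / rank ANCOVA (final ranks on arm and baseline ranks). Power in %:

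| Shape | rho 0.3 | rho 0.5 | rho 0.7 |
|---|---|---|---|
| Normal | 52 / 72 / 71 | 67 / 80 / 79 | 87 / 92 / 90 |
| Mild skew | 60 / 72 / 83 | 77 / 80.5 / 89 | 93 / 93 / 97 |
| Strong skew | 87 / 76 / 99 | 96 / 82 / 99.6 | 99.8 / 92 / 100 |
| t, 3 df | 80.5 / 78 / 93 | 91 / 84.5 / 96.5 | 99 / 93 / 99.4 |

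Size under the null was 4.6–5.7, 3.6–5.2 and 4.6–6.0% respectively. A repeat with 1,500 replicates gave, for Mann-Whitney v rank ANCOVA, 52 v 71, 66 v 78 and 90 v 92% (normal) and 63 v 84, 76 v 89 and 92 v 97% (mild skew). The two runs agree within about 3 points; the conclusion quotes the repeat.

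**Step 3: where the gain ends.** Smaller shifts keep power below 100%. Mann-Whitney v rank ANCOVA:

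- rho 0.8, 0.35 SD: normal 76 v 76%; t 95.6 v 94.8%
- rho 0.9, 0.25 SD: normal 77 v 74%; t 96 v 93%; mild skew 85 v 88%
- rho 0.95, 0.15 SD: normal 62.5 v 57%; t 89 v 81%; mild skew 74 v 73%

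**Step 4: interval width.** The interval that belongs with the planned test is Hodges-Lehmann on change. Median 95% half-widths in SD units, Hodges-Lehmann v linear ANCOVA:

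| Shape | rho 0.3 | rho 0.5 | rho 0.7 |
|---|---|---|---|
| Normal | 0.481 v 0.385 | 0.406 v 0.349 | 0.314 v 0.287 |
| Mild skew | 0.437 v 0.380 | 0.365 v 0.345 | 0.282 v 0.284 |
| Strong skew | 0.311 v 0.359 | 0.252 v 0.324 | 0.189 v 0.264 |
| t, 3 df | 0.344 v 0.346 | 0.290 v 0.314 | 0.225 v 0.259 |

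Neither is narrower throughout, and they estimate different quantities.

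**Step 5: pooling.** True null, normal data, rho 0.3–0.7, five imputations, 3,000 replicates. Rejection rates at 5%, 20% and 40% missing:

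| Rule | 5% missing | 20% missing | 40% missing |
|---|---|---|---|
| Median of five p-values | 5.0–5.7% | 7.5–8.3% | 10.1–12.4% |
| Mean of five p-values | 4.7–5.3% | 5.3–6.6% | 5.8–6.9% |
| Average the imputed values, test once | 5.2–6.6% | 10.4–10.9% | 15.3–21.1% |

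Across 5–40% missing, Rubin-pooled P(X>Y) rejects 4.1–5.8% and Rubin-pooled rank ANCOVA 3.8–5.5%. With 20% missing and a 0.5 SD shift, power for pooled P(X>Y) on change v pooled rank ANCOVA is 46 v 58, 58 v 66 and 78 v 81% for normal data at rho 0.3, 0.5 and 0.7. These runs assume values missing completely at random, in equal numbers per arm.

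**The case against.** The strongest reply is that nothing here is an error. Mann-Whitney on change is valid in a randomised comparison, it suits data the SAP calls nonparametric, and the gain from adjustment depends on a correlation and a shape that the documents do not give. That stands: the power point is conditional. The missing difference with a CI does not depend on those assumptions.

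A reader might infer that a linear ANCOVA interval would be narrower whatever the distribution. It is 6–20% narrower than a mean-change interval at rho 0.3–0.7, but the SAP does not plan a mean-change interval. Against Hodges-Lehmann it is wider under strong skew and level or wider for t with 3 df. Linear ANCOVA also loses power there: 76% v 87% for Mann-Whitney under strong skew at rho 0.3.

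It can also be said that using a rank model for the p-value and a linear model for the interval is heavier than the defect. The two disagree on significance in about 4–24% of trials with complete data in these settings. That is a real cost.

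Finally, the SAP is written in the past tense. Changing the primary test once results are known would be a post hoc choice. That objection is accepted and shapes the fix.

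**Conclusion.** The point holds as a cheap improvement. For the primary outcome the plan makes one post-baseline comparison of the arms, uses baseline intake only by subtraction, and gives no between-group difference with its precision. At 50 per arm and an assumed 0.5 SD shift, baseline-adjusted rank analysis gains about 19 points of power at rho 0.3 (52 v 71%) and 12 at 0.5 (66 v 78%) for normal data, and 21 and 13 points under mild skew (63 v 84%, 76 v 89%). The gain is small or nil by rho of about 0.7–0.8 and reverses at 0.9 for normal or heavy-tailed data.

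Two stronger readings are not supported. One is that the planned intention-to-treat result is wrong because of pooling. The SAP names no faulty rule, its wording suggests that separate results were combined rather than imputed values averaged, and the effect is small with little missing data. The other is that the power argument extends to body weight and handgrip strength; it would fail there if their baseline-final correlations are around 0.9 or above.

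The pooling checks also leave unequal missingness untested. In a trial sized on mortality, unequal losses through death are foreseeable.

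**What to change.** For energy (kcal/kg) and protein (g/kg) intake only, in each imputed data set:

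1. Test the arms by regressing the ranks of the final value on arm and baseline ranks.
2. Estimate the difference by regressing the final value on arm and baseline value with HC3 standard errors, and report it in kcal/kg and g/kg with a 95% CI.
3. Pool both by Rubin's rules, and say so.

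Where intake is clearly skewed or heavy-tailed, also give a Hodges-Lehmann difference with CI on change in the per-protocol (completer) analysis, and state that it estimates a different quantity.

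If the data have not been analysed, the adjusted analysis may be primary, with Mann-Whitney on change as a sensitivity analysis. If they have, as the past tense suggests, keep Mann-Whitney on change as the planned test and report the adjusted analysis as a labelled reanalysis. Wherever Mann-Whitney is pooled over imputations, pool P(X>Y) with its variance.

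For body weight and handgrip strength, keep Mann-Whitney on change and add a between-group difference with 95% CI.

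The cost is a few lines of text and two regressions per intake outcome on data already collected. The SAP should also say in advance how a disagreement between the rank p-value and the linear interval will be read.
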